**STUDY PROCEDURES:**

We will contact each family prior to the MRI visit to provide information about the study. Written consent will be obtained on the day of the exam. At that time, absence of exclusion criteria will be confirmed with a questionnaire and pregnancy testing for all females of child bearing potential will be completed prior to imaging.

MR-PFT (Exp 1) and MRE (Exp 2) exams will each be performed once per subject on a 1.5T GE HDx MRI scanner (General Electric; Milwaukee, WI). Subjects will be required to fast (NPO) for four hours prior to MR imaging. Subjects will be weighed and measured immediately prior to imaging. The IV will be placed by the MRI technologist at the beginning of the imaging examination. The patient will then be placed into the scanner and the MRE passive driver will be placed on their abdomen. The patient will be provided with standard hearing protection and entertainment options (video goggles). All pre-secretin imaging will then be performed. A study team physician or a Radiology Department nurse will then inject the secretin through the IV and all post-secretin imaging will be performed. Once imaging is completed, the patient will be removed from the scanner and the IV will be removed.

Anticipated duration of MR imaging is approximately 35 minutes scan time (total 50 min in room time). Scan time pre-secretin (5 sequences, including MRE) is approximately 20 minutes. Scan time post-secretin (sequences for MR-PFT) is approximately 15 minutes. The additional time is required for positioning, localization, sequence planning, and secretin injection. The MRI examinations can be terminated at any time upon request of the participant. All MR imaging will be done as scheduled appointments.

All images will be maintained in the research PACS environment. Data that will be saved will include participant number, age at time of examination, and MR data. Identifying data will be saved in a password-protected database.

*Facilities:*

Visits will be conducted within the main clinical CCHMC Radiology Department. The MR scanner being used is owned and operated by the CCHMC Department of Radiology.

*Radiologist Review of Images:*

The imaging protocol used in this study includes only the minimum scanning needed to achieve the research objective outlined by the study investigator. No report will be generated or supplied to the research participants. However, all scans performed for this project will be reviewed for gross abnormalities by a board-certified or board-eligible radiologist. Although no diagnosis will be made, in the event that abnormal findings are identified, the PI will be informed and will assume responsibility for notifying the participant. In this case written documentation that an abnormal finding has been identified will be provided to the participant.

**DATA ANALYSIS/METHODS:**

*Statistical analysis:*

Statistical analyses will be tailored to our study purposes as follows:

**Collect normative data for volume of secreted fluid in response to secretin administration in a representative sample of healthy pediatric controls.**

Means, standard deviations and 95% confidence intervals will be used to summarize study population secreted volumes. Linear regression will be used to assess for significant correlation between subject age and secreted volume. Similar regression models will be used to test other body-size covariates such as BSA, BMI, etc. If feasible, a quantile regression will be performed of secreted volume or BSA normalized secreted value to attempt to quantify normal range as a function of age, BMI, etc.

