### **RECRUITMENT & CONSENT OF PARTICIPANTS:**

*Subject Recruitment:*

Recruited subjects will have no history of pancreatic disease and will be identified through review of patients presenting for non-abdominal imaging examinations. Patients presenting for musculoskeletal MRI examinations will likely be the major source for recruited patients. In the last 2 years, 1297 musculoskeletal MR examinations have been done in pediatric patients, ages 6 -15 years, at our institution, providing a ready source for recruitment. Subjects may additionally be recruited through public recruitment using existing clinical trial recruitment services at CCHMC, including advertising within our institution to raise awareness of the study. CCHMC employees may be invited to enroll their children in the study; they would be invited by the research coordinator. Subject charts will be reviewed for evidence of pancreatitis or other pancreatic disease prior to/during enrollment. Following initial screening, subjects will be contacted by the study coordinator or an investigator and enrolled after informed consent is obtained. During enrollment, absence of exclusion criteria will be confirmed with a questionnaire completed prior to imaging.

50 evaluable subjects will be recruited evenly divided as follows:

25 subjects age 6-11.9 years

25 subjects age 12-15.9 years

*Inclusion Criteria:*

1. Subjects between the ages of 6 and 15.9 years.
2. Subjects without a documented history of (or suggestive of) pancreatic disease.

*Exclusion Criteria:*

1. History of pancreatic disease, liver disease, intra-abdominal neoplasm, abdominal inflammatory process such as inflammatory bowel disease (IBD), or systemic illness that may affect pancreatic state (e.g. cystic fibrosis).
2. Subjects with surgical hardware/implanted devices making them ineligible for MRI (e.g. pacemaker or other implanted medical device not approved for MRI).
3. Subjects who require any form of sedation or general anesthesia for MRI.
4. Subjects unable to breath-hold for the required 15-20 second imaging sequence.
5. Subjects who are pregnant or less than 12 months post-partum.

*Process of obtaining Consent:*

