**Collect normative data for pancreatic stiffness as measured by MR elastography.**

Means, standard deviations and 95% confidence intervals will be used to summarize study population pancreatic parenchymal stiffness. Linear regression will be used to assess for significant correlation between subject age and parenchymal stiffness. Similar regression models will be used to test other body-size covariates such as BSA, BMI, etc.

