**Assess the effect of secretin on the visibility of the pancreatic duct.**

Frequencies and rankings will be compared with Fischer exact test and Wilcoxon rank sum tests to compare visualization of the pancreatic duct pre- and post-secretin.

*Power calculation:*

To establish relationship between secreted fluid volume and subject body size or age, we base a power calculation on analysis of MR-PFT data in 19 CP patients and the assumption that secreted volume is correlated with age in this sample of patients. In a linear regression analysis of these patients, the observed residual standard error is approximately 39, with an  $R^2 \sim 0.40$ . The observed regression coefficient is 5.274, and standard deviation of predictor age is  $\sim 5.816$ . If this holds in a general population, we require at least 15 normal subjects to have a significant regression coefficient at 0.05 level, and 80% power.

Additionally, from the previously reported study of normal adult patients by Mensel et al. [25], the coefficient of variation (CV) of secreted volume (TEV in the paper) at various time points from secretin injection ranged from 0.30 to 0.51. Given that we plan to enroll subjects in two age groups (6-11.9 and 12-15.9 years old), 25 subjects in each age group will provide 80% chance that the 95% confidence interval of mean secreted volume will be within 12% to 20% of the mean value, depending on the actual CV observed.

Therefore, we plan to enroll a total of 50 evaluable subjects in the study to meet both needs above.

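### Quantile regression is the only analysis tied to a normal range; if it supplies outer reference limits at n = 50, the band is too narrow on average

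*Combined protocol and SAP*

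**What the plan says.** The Abstract makes determining the normal range of secreted fluid volume an aim, and the Background makes establishing such ranges the overall hypothesis. In DATA ANALYSIS/METHODS, Statistical analysis, one sentence serves that aim for secreted volume: if feasible, "a quantile regression will be performed of secreted volume or BSA normalized secreted value", the purpose being "to attempt to quantify normal range as a function of age, BMI, etc". The sentence gives no percentile levels, closed list of covariates, criterion for feasibility or fallback.

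The other planned analyses are not described as ranges. For volume, "Means, standard deviations and 95% confidence intervals will be used to summarize study population secreted volumes", and linear regression tests association with age and body size. Stiffness has the same summaries and regressions, and no range method.

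On size, the recruitment section says "50 evaluable subjects will be recruited evenly divided as follows", with 25 children aged 6-11.9 and 25 aged 12-15.9 years. The Power calculation rests on the age slope and on the precision of a mean, and ends: "we plan to enroll a total of 50 evaluable subjects in the study to meet both needs above".

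**The concern.** A reference range usually means outer percentiles, such as the 2.5th and 97.5th. Quantile regression estimates these from the few observations near each tail. With 50 children there is about one per tail, so the fitted limit follows the most extreme children in the sample and tends to lie inside the true percentile. Each added covariate gives the line more freedom to follow them. The result is bias towards a narrow band as well as imprecision.

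The software returns a line at n = 50 regardless, so nothing in the output warns the analyst. The protocol wants these data as a baseline for later studies of children with suspected chronic pancreatitis or pancreatic insufficiency. A band that is too narrow would carry an excess of healthy children classed as outside normal into that comparison. For secreted volume the lower limit matters most, because insufficiency means reduced secretion.

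**Working it through.** **The plan's own figures.** Both reproduce, and neither concerns an outer percentile.
- Age slope: the noncentrality parameter is sqrt(n) x 5.274 x 5.816 / 39, two-sided 0.05. Power is 77.1% at n = 14 and 80.4% at n = 15, so the stated 15 reproduces.
- Precision of the mean, 25 per group: 1.96 x CV / sqrt(25) gives 1.96 x 0.30 / 5 = 11.8% and 1.96 x 0.51 / 5 = 20.0%. This is the stated 12%-20%, as a plain half-width without the stated 80% chance.

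**Tail counts.** 50 x 0.025 = 1.25 children beyond each limit; within one age group, 25 x 0.025 = 0.625.

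**Precision of a limit.** For normal data, n = 50 and the 2.5th percentile:
- Non-parametric: sqrt(0.025 x 0.975 / 50) / 0.0584 = 0.378 SD.
- Parametric: sqrt((1 + 1.96² / 2) / 50) = 0.242 SD.
- Variance ratio: (0.378 / 0.242)² = 2.4. Finite-sample simulation gives a similar or somewhat smaller ratio (about 2.2 in one run with one covariate).

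**Bias of the band, by simulation.**
- From the plan: n = 50, half in each age band; slope 5.274 per year; residual SD 39, or a CV of 0.40 (inside the plan's 0.30-0.51).
- Assumed: limits at the 2.5th and 97.5th percentiles, ages uniform within each band, mean volume 100 mL at age 11, and a second covariate that is unrelated noise, standing in for BMI.
- Each of 2,000 replicates per setting fits linear quantile regression at 0.025 and 0.975, then counts the share of 3,000 new healthy children outside the band.

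| Covariates | Errors | Mean share excluded (nominal 5%) | 10th-90th percentile of studies | Studies above 5% |
|---|---|---|---|---|
| 1 | normal, SD 39 | 8.6% | 4.0%-13.7% | 81% |
| 1 | normal, CV 0.40 | 8.6% | 4.0%-14.2% | 81% |
| 1 | lognormal, CV 0.40 | 8.6% | 4.0%-14.1% | 82% |
| 2 | normal, SD 39 | 11.6% | 6.3%-17.5% | 96% |
| 2 | normal, CV 0.40 | 11.5% | 6.3%-17.2% | 96% |
| 2 | lognormal, CV 0.40 | 11.6% | 6.2%-17.5% | 95% |

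The Monte Carlo standard error is about 0.1 percentage point. Gamma errors give the same picture (all shapes: 8.3%-8.7% with one covariate, 11.3%-11.8% with two). Below the lower limit alone, the share is 4.1%-5.9% instead of 2.5%.

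In the constant-SD setting the result does not depend on the values 100, 5.274 or 39. Adding a linear function of age to the volumes, or rescaling them, moves the fitted quantile lines in exactly the same way.

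**Other percentile choices, n = 50.** A 5th-95th band excludes about 13%-16% instead of 10%; a 10th-90th band about 23% instead of 20%.

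**Alternative methods on the same kind of data (nominal 5% in total, 2.5% below).**
- Fixed log scale, one covariate, normal errors: 5.2% below the lower limit, against 4.1% for quantile regression. In about 25%-34% of these samples a non-positive volume prevents the log from being taken.
- Untransformed scale, lognormal errors: only 0.3% below the lower limit.
- Transformation estimated from the data (Box-Cox): 5.1%-6.1% excluded in total and 2.4%-4.0% below the lower limit across all settings, against 4.1%-5.9% below it for quantile regression.

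**The case against.** The plan never commits to outer percentiles or to a band labelled 95%. It also hedges, and an analyst with one child per tail could reasonably judge outer quantiles infeasible. The study is a pilot meant to give preliminary data, and no diagnostic cut-off is planned from these 50 children. All of this stands. A reader might infer that the stated method will give a false-positive rate twice the stated one. The documents do not support that, because no rate is stated, and the near doubling arises only under the assumed 2.5th and 97.5th percentiles. The hedge does not remove the problem, however: feasibility is undefined and no other range method is named.

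A second objection is that a parametric range exchanges variance for dependence on shape. This also stands. A fixed log transformation is no better than quantile regression at the lower limit under normal errors, and a total near 5% can hide opposite errors in the two tails. It rules out a fixed transformation as the remedy but not an estimated one.

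Two smaller points are fair. The constant-SD setting is implausible for the youngest children: at age 6 the mean is 100 - 5 x 5.274 = 73.6, and 73.6 - 1.96 x 39 = -2.8 mL. The constant-CV, lognormal and gamma settings give the same exclusion for quantile regression. And a quantile line passes through as many observations as it has coefficients at any quantile, including the median, so that fact alone shows no bias. The bias comes from having so few children beyond the line.

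**Conclusion.** The concern holds conditionally. If quantile regression supplies outer reference limits from 50 children, the band is too narrow on average. Under assumed 2.5th and 97.5th percentiles it excludes about 8.5% of healthy children with one covariate and 11.5% with two, instead of 5%, with about 4%-6% instead of 2.5% below the lower limit. The relative error shrinks for less extreme percentiles. The size rests on the assumed percentiles and on one or two linear covariates; it barely depends on the error distribution. Single studies vary widely around these averages.

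The documents do not show that the plan will publish a mislabelled 95% range or that patients will be misclassified by it. They show an aim to establish a range, one method attached to it, and no percentiles, covariate limit or fallback to keep that method where 50 children can support it. This should be corrected before analysis; the hedge and the pilot status keep it from being graver.

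**What to change.** In DATA ANALYSIS/METHODS, under secreted volume:
1. State the percentiles that define the normal range.
2. Take the outer limits from a regression of secreted volume on a small, pre-named set of age or size covariates. Use t-based prediction limits on a scale estimated from the data (for example Box-Cox) with a residual check, not a fixed log. Box-Cox needs positive values, so state in advance how a zero or negative volume is handled, for example by a shift.
3. Report the lower and upper limits separately, each with a bootstrap confidence interval that repeats the estimation of the transformation.
4. Keep quantile regression for the median and quartiles, as a check on shape.

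The cost is SAP wording and a little code; no extra children, scans or secretin are needed. The downside is that the limits depend on the fitted shape. The lower tail can still be off (about 2.4%-4.0% in simulation with an estimated transformation, and further off with a wrongly fixed one). Report this as a limitation of a preliminary data set.

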**Collect normative data for pancreatic stiffness as measured by MR elastography.**

Means, standard deviations and 95% confidence intervals will be used to summarize study population pancreatic parenchymal stiffness. Linear regression will be used to assess for significant correlation between subject age and parenchymal stiffness. Similar regression models will be used to test other body-size covariates such as BSA, BMI, etc.

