**ABSTRACT:**

**Introduction/Methods:** Pancreatic fibrosis is the end stage of chronic pancreatitis (CP), which leads to loss of acinar volume and secretory capacity, and ultimately pancreatic insufficiency (PI). CP and congenital PI affect the pediatric population, and are both increasingly recognized in children. PI has serious negative implications on a child's growth and health but, if diagnosed early, PI can be treated, minimizing the detrimental effects of PI. Currently, direct pancreatic function testing (PFT) via collection of pancreatic fluid is the "gold standard" for diagnosis of PI but it is an invasive testing that may require sedation or general anesthesia. Magnetic resonance cholangiopancreatography (MRCP) with secretin administration (MR-PFT) and MR elastography (MRE) may allow non-invasive, and potentially early diagnosis of CP and PI. Currently, however, normative data with which to compare MR-PFT and MRE results in pediatric patients with suspected CP/PI is not available. **Aims:** Herein, we propose to determine the normal range for secreted pancreatic fluid volume in response to secretin administration and determine the normal range for pancreatic parenchymal stiffness in a pediatric population that is not affected by pancreatic disease. Additionally, we will assess visibility of the pancreatic duct pre and post administration of secretin. To date, we have validated our MRCP technique and have successfully performed both MR-PFT and MRE in CP patients; however normative data is essential for validation of our non-invasive technique. **Conclusion:** Normative pediatric data derived from this study will provide a baseline against which future studies of pediatric patients with suspected CP and PI can be assessed. Additionally, the techniques described herein might also be leveraged in the future in the adult population.

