**PURPOSE OF STUDY:**

**Collect normative data for pancreatic state (the size, volume, anatomy, biliary and vascular structures) as well as the volume of secreted fluid in response to secretin administration in a representative sample of healthy pediatric controls.**

**Determine secreted volumes:** *Hypothesis 1.* Total secreted fluid volume as measured by MR-PFT will correlate with subject size and age. *Exp 1.* MR-PFT will be performed in 50 healthy pediatric subjects including 25 subjects ages 6-11.9 years and 25 subjects 12-15.9 years. Secreted volumes will be correlated with subject age and height, weight, body mass index and body surface area.

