**Collect normative data for pancreatic stiffness as measured by MR elastography.**

*Hypothesis 2.* Pancreatic parenchymal stiffness in the pediatric population will fall in a normative range similar to adult norms and will not depend on subject age or size. *Exp 2.* Pancreatic parenchymal stiffness will be measured in the same healthy cohort of 50 healthy pediatric subjects including 25 subjects ages 6-11.9 years and 25 subjects 12-15.9 years.

**Assess the relationship between pancreatic exocrine function, pancreatic stiffness and pancreatic parenchymal volume.** *Hypothesis 3.* Pancreatic exocrine function as measured by MR-PFT and pancreatic stiffness as measured by MRE will be dependent on pancreatic parenchymal volume. *Exp 3.* Secreted fluid volumes as measured by MR-PFT and pancreatic

stiffness as measured by MRE will be correlated with volumetric measurements of pancreatic parenchymal volume.

**Assess the effect of secretin on the visibility of the pancreatic duct.** *Hypothesis 4.* A subjective, blinded assessment of pancreatic duct visibility pre-and post-secretin will show an increase in visibility on post-secretin images.

We will also store this data to identify normative values in controls for pancreatic and any other gastrointestinal parameters in MRCP.

*Significance and Innovation:*

Our study will add significant information to the existing literature regarding diagnosis and staging of CP, and will set the foundation for using MR as a non-invasive biomarker for CP/PI in pediatrics. Our study is novel because it will investigate the use of MRI for assessing pancreatic anatomy, function, and stiffness in the pediatric population. It will also shed light on gastrointestinal anatomy and function in pediatric healthy controls which has not yet been described in the literature. Moreover, the results of our study will fill a knowledge gap regarding normal secretory function of the pancreas in children.

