In preparation for this study, we developed a protocol to measure pancreatic fluid volume secreted in response to secretin administration, confirmed feasibility of pancreatic stiffness measurements by MRE and analyzed our experience with MR in pediatric patients with pancreatic disease, primarily CP. We have a cohort of CP patients that have undergone MRCP with the proposed study protocol and we will continue to collect data on CP patients that undergo MR studies. The overall aim of this pilot-study is to collect MR-PFT and MRE data in a small group of normal pediatric subjects (with no history of pancreatic disease, CP/PI, or intestinal disease) to serve as a preliminary data set for a subsequent comparative study of MR-PFT and MRE in children with CP. The ultimate aim is to provide results that would position non-invasive MR studies as an accurate, sensitive, and specific alternative to standard modalities of CP diagnosis and therapy monitoring (endoscopic PFT (ePFT), endoscopic

retrograde cholangiopancreatography (ERCP), endoscopic ultrasound (EUS), and biopsy). **Our overall hypothesis is that normative ranges can be established for total secreted pancreatic fluid volume as measured by MR-PFT and for pancreatic stiffness as measured by MRE and that secreted volumes but *not* pancreatic stiffness will depend on subject age and size.**

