#### Pre-Secretin:

Axial 3D T1 GRE (LAVA)  
Axial fat saturated T2 fast spin echo (FSE)  
Axial 3D GRE magnetic resonance elastography (MRE)  
Axial T2 map  
Coronal 3D fast relaxation fast spin echo (FrFSE)  
Coronal fat saturated T2 SSFSE

Post-Secretin:

Coronal fat saturated T2 SSFSE at 1, 5, 10 and 15 minutes after Secretin injection

Coronal 3D FrFSE

*MR post-processing:*

MR-PFT:

Total secreted fluid volume in response to secretin will be determined from the pre- and post-secretin coronal T2 SSFSE using commercially available software (ImageJ, MatLab) by selecting a signal intensity threshold which isolates intraluminal fluid in the duodenum and proximal jejunum. A region of interest will then be drawn on each image inclusive of thresholded pixels, to determine the area (mm^2) of fluid signal. The area of fluid signal on each image will then be multiplied by the image slice thickness and all slice values will be summed to determine a fluid volume over the entire imaged volume.

MRE:

MR elastography images will be post-processed using software leased from Resoundant (Rochester, MN) with pancreatic parenchymal stiffness expressed as a mean stiffness (kPa) for the pancreatic neck, body, and tail.

Parenchymal volume:

Pancreatic parenchymal volume will be measured by manual segmentation of the pancreas using commercially available software (MIM, MIM Software Inc.; Cleveland, OH).

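### The aim is a normal range for secreted volume and for pancreatic stiffness, but the plan commits to no analysis that yields one

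*Combined protocol and SAP*

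**What the plan says.** Three places make a normal range the product of the study. The Abstract aims to "determine the normal range for secreted pancreatic fluid volume in response to secretin administration and determine the normal range for pancreatic parenchymal stiffness". Hypothesis 2 in Purpose of Study states that "Pancreatic parenchymal stiffness in the pediatric population will fall in a normative range similar to adult norms". The overall hypothesis in Background is that "normative ranges can be established for total secreted pancreatic fluid volume as measured by MR-PFT and for pancreatic stiffness as measured by MRE".

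Data Analysis/Methods then plans the following.

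- **Stiffness:** "Means, standard deviations and 95% confidence intervals will be used to summarize study population pancreatic parenchymal stiffness", plus linear regressions on age and on body-size measures.
- **Secreted volume:** the same summaries and regressions, and then "If feasible, a quantile regression will be performed of secreted volume or BSA normalized secreted value to attempt to quantify normal range"; the range is meant to vary with covariates such as age and body size. No quantiles, feasibility criterion or alternative are given.

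The Power calculation sizes the study on a regression slope and on the precision of the mean secreted volume. It does not address a range, and it does not address stiffness.

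**The concern.** A normal range describes where individual healthy children lie. A mean with its confidence interval describes where the average lies, and a regression test says whether the average changes with age or size. Neither is a range unless the plan says how to turn it into one.

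For stiffness that step is missing, so the first half of Hypothesis 2 has no stated analysis. For volume it depends on a method that 50 subjects may not support. The data are meant "to serve as a preliminary data set for a subsequent comparative study of MR-PFT and MRE in children with CP". That study would need limits and a record of how they were derived. As written, the pilot could finish with no stiffness limits, and with volume limits whose method was chosen after the data were seen.

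**Working it through.** **1. What the plan's own sample-size figures are about.** With 25 children per age group and the adult CVs of 0.30 to 0.51, the half-width of the 95% CI of the mean is 1.96 × CV / √25:

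- 1.96 × 0.30 / 5 = 11.8%
- 1.96 × 0.51 / 5 = 20.0%

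These match the plan's 12% to 20% as half-widths at the assumed CV. The attached 80% chance does not reproduce, but that is a separate matter. The regression inputs (slope 5.274, age SD 5.816, residual SE 39) give R² = (5.274 × 5.816)² / [(5.274 × 5.816)² + 39²] = 940.9 / 2461.9 = 0.38, in line with the stated 0.40 or so. Both figures concern a mean or a slope, not a limit.

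**2. Is the CI of the mean a usable range?** Its half-width in SD units is t/√n. Under normality, an interval that wide centred on the true mean holds 2Φ(t/√n) − 1 of children:

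- n = 25: 2.064 / 5 = 0.413 SD, which holds 32%
- n = 50: 2.010 / √50 = 0.284 SD, which holds 22%

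A 95% range should hold 95%.

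**3. Can quantile regression deliver 2.5% limits at n = 50?** The number expected beyond each limit is 0.025 × 50 = 1.25. The chance of none beyond a given limit is 0.975^50 = 0.28. The plan's caution is justified, and that is why a fallback is needed.

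**4. What would limits from the planned age regression look like?** Assume ages spread evenly within each stratum (25 in 6–12, 25 in 12–16). The mean age is 11.5, the variance is 0.5 × (36/12 + 16/12) + 2.5² = 8.417, and the SD is 2.90. For a limit taken as fitted value ± 1.96 residual SDs, the 95% CI half-width is 1.96 × √(1/50 + d²/50 + 1.96²/(2 × 48)), where d is the distance from mean age in age SDs.

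| Age | d | Half-width (residual SD) | At residual SE 39 |
|---|---|---|---|
| 11.5 | 0 | 0.48 | 19 units |
| 6 | 1.896 | 0.71 | 28 units |
| 16 | 1.551 | 0.64 | 25 units |

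A cohort-wide interval without covariates, as for stiffness, has 1.96 × √(1/50 + 1.96²/(2 × 49)) = 0.48 SD. The documents give no stiffness SD, so this cannot be put in kPa.

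**5. Illustration only: why volume limits should come from the regression.** Suppose the slope and residual error from the 19 CP patients held in healthy children, with normal errors. A pooled SD would be √(39² + (5.274 × 2.90)²) = 41.9, and mean − 1.96 SD would lie 82.1 units below the cohort mean at every age. The share of healthy children below it would be:

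- age 6: Φ((−82.1 + 29.0)/39) = 8.7%
- age 16: Φ((−82.1 − 23.7)/39) = 0.3%

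Formed by age stratum instead:

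- younger (SD 40.06, limit 78.5 below the stratum mean): 5.4% at age 6, 0.8% just under 12
- older (SD 39.47, limit 77.4 below the stratum mean): 4.3% at age 12, 1.2% just under 16

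The target is 2.5% throughout.

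**The case against.** **The regression is already there.** The linear regression of volume on age is planned without the feasibility condition, and a fitted line with its residual SD is what age-specific limits need. This stands. For volume the gap is an unstated last step, which makes the fix cheap. It does not close the gap, because the plan uses the regression only to test for correlation.

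**A reader can form mean ± 1.96 SD.** True, but the plan does not say this will be done or called the normal range. For volume, an age-blind range would also sit badly with the plan's own expectation that "Total secreted fluid volume as measured by MR-PFT will correlate with subject size and age".

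**It is a pilot, and the data are kept.** Background describes a small preliminary data set, nobody is diagnosed from its limits, and the de-identified data are kept, so a later team could derive limits itself. This lowers the severity. It does not supply an analysis for the study's own stated aim.

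**Readings the documents do not support.** A reader might infer that the study will misclassify about 9% of its youngest children. It will not: the plan never proposes an age-blind limit, and the illustration borrows slope and error from 19 CP patients whose age SD (5.816) is about twice this cohort's (2.90). No mean volume is given either. If the pooled SD of 41.9 went with a CV of 0.51, the mean would be about 82 and the pooled limit about zero, so the normal model would itself be doubtful; at CV 0.30 (mean about 140) that problem does not arise. A reader might also infer that no range method exists at all, or that 50 is too few. Quantile regression is named for volume, and a pilot can report imprecise limits if it says that they are imprecise.

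**Measurement definitions are a separate question.** The plan images at several times ("Coronal fat saturated T2 SSFSE at 1, 5, 10 and 15 minutes after Secretin injection"), and which of them defines secreted volume affects every volume analysis, not only the range.

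**Conclusion.** The point holds. A normal range for two measures is the stated aim; for stiffness no range analysis is named, and for volume the only one is conditional and has no fallback. This follows from the text and depends on no assumed number. The planned CI of the mean is no substitute (22% to 32% coverage under normality), and empirical 2.5% limits at n = 50 rest on about one child per tail. The half-widths of 0.48 to 0.71 SD assume normal residuals of constant spread, a linear age effect and ages even within strata. The misclassification percentages are illustrative and do not carry the conclusion. The plan should be changed, but the gap does not invalidate a pilot.

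**What to change.** In the secreted-volume and stiffness paragraphs of Data Analysis/Methods, commit to a 95% reference interval (2.5th and 97.5th percentile limits) for each measure as the main normative output, with a 95% CI on each limit.

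- **Secreted volume:** take age-specific limits from the linear regression on age already planned, with the BSA model as secondary. State in advance how residuals will be checked and, if needed, transform with a method that allows zeros, since a thresholded volume can be zero. Keep quantile regression as exploratory.
- **Stiffness:** give one cohort-wide interval, in line with Hypothesis 2, with the age-conditional interval as secondary. Set it beside the published adult range, so that the comparison in Hypothesis 2 is actually made.
- **Both:** keep the mean, SD and CI of the mean as description.

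The cost is a few sentences and a few lines of code, with no new data and no change to the sample size. The downside is that the limits depend on a distributional form and are imprecise, about 0.48 SD at mid-age and 0.64 to 0.71 SD at the age extremes. The report should state this alongside the pilot status.
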